risk in young subjects; www.FDA.gov). Since its approval by FDA for chronic pain treatment, duloxetine has been increasingly used in clinical settings. **Fourth**, among SNRIs including milnacipran and venlafaxine, duloxetine (60 mg, oral) has a pharmacokinetic profile that favors a chronic course of treatment with minimal day-to-day dose adjustment, including about 6 hours to reach the peak plasma level, an elimination half-life of 8-17 hours (average 12 hours), and a 50% oral bioavailability (www.FDA.gov). In comparison, milnacipran involves a more complicated titration schedule and is approved for fibromyalgia treatment whereas venlafaxine is used off-label for pain treatment and has a rather short half-life requiring 2-3 daily doses (www.FDA.gov). Therefore, we choose to add duloxetine (generic formula; daily dosing) to an opioid therapy in this clinical study. We expect that this combination therapy will enhance opioid analgesia and reduce overall opioid use, thereby diminishing opioid dependence/withdrawal and OIH.

II. SPECIFIC AIMS

This study has two specific aims:

1. To examine changes in VAS scores and to determine total versus rescue opioid use (primary outcomes) after each treatment
2. To compare secondary outcomes including a) side effect profile, b) dropout rate, c) functional status, d) physiologic opioid dependence, e) OIH, and f) urine drug screening

III. SUBJECT SELECTION

a. Inclusion/Exclusion Criteria

Inclusion Criteria:

1. Subject is 18-70 years old.
2. Subject has chronic neck or back pain for at least 3 months.
3. Subject has a VAS ≥ 6 .
4. Has not taken duloxetine in the last 3 months.
5. Has not taken an opioid in the last 3 months, but has taken one in the past without sufficient pain control OR has never taken opioids but has failed at 3 (or more) non-opioid treatments.

Exclusion Criteria:

1. Subject has major psychiatric disorders requiring recent hospitalization (within 3 months) such as major depression, bipolar disorder, schizophrenia, anxiety disorder, or psychotic disorder.
2. Subject is using illicit drugs or alcohol detected by urine toxicology/drug screen.
3. Subject has a history of alcohol use disorder within 6 months.
4. Subject is pregnant or lactating/breast feeding.
5. Subject is allergic to morphine or duloxetine.
6. Subject is on an antidepressant including SNRI, SSRI, tricyclic antidepressant.
7. Subject has a history of suicidal attempts or current suicidal ideation.

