Seven office visits (screening visit, weeks 1, 3, 5, 7, 9, and end of week 10) and four follow up phone calls (weeks 2, 4, 6, and 10) will be used to collect data. Since this is a prospective study, we will be able to first determine baseline quantitative sensory testing (QST) and VAS pain score, followed by assessing their longitudinal changes at each office visit. To assess OIH, QST will be performed at each office visit before subject takes the next dose of the study drugs. We will also measure plasma morphine concentration during the titration and maintenance phase to help validate morphine intake.

Urine Screening

Subjects who are using illicit drugs detected by urine toxicology/drug screen including stimulants, benzos, alcohol, opioid (other than the study opioid), cocaine will be withdrawn from the study.

Given the increasing use of marijuana in general population and the knowledge of a minimal impact of occasional marijuana use on opioid effects, we will use the following plan to monitor marijuana use.

- a. If subjects test positive for marijuana use at the initial screening, the subjects will be given the chance to have a second urine test in one week. If the second test is negative, subjects will be allowed to participate in the study. If the urine test is positive, subjects will be withdrawn.
- b. During the study, subjects take a urine drug test at each office visit. Similarly, if the subject tests positive for marijuana use at one of these office visits, the subject will be given the chance to have a second test in one week while continuing the study. If the second test is also positive, the subject will be dismissed from the study with a proper monitoring and management of withdrawal symptoms.

Screening Visit

1. Subject will meet with a study physician to review pain and medical history to confirm inclusion/exclusion criteria
2. Informed consent will be obtained by a study physician
3. Vital signs (blood pressure, oxygen saturation, and pulse) will be taken
4. Urine sample will be collected for drugs of abuse (DOA) and pregnancy test
5. The following questionnaires will be completed: Pain Questionnaire, Short-form McGill Pain Questionnaire (SF-MPQ2), Short-form 36 (SF-36), Beck Depression Inventory (BDI-II), Prescription Drug Use Questionnaire (PDUQ), Screener and Opioid Assessment for Patients with Pain- Reversed (SOAPP-R) and Anxiety Sensitivity Index (ASI)
6. Sensory test at QST site
7. QST testing

Visit 1

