1. Vital signs will be taken
2. Urine sample will be collected for DOA and acetazolamide/creatinine measurement
3. Provide study medication and review medication instructions, daily pain log, and daily medication log
4. The following questionnaires will be completed: Pain Questionnaire, Short-form McGill Pain Questionnaire (SF-MPQ2), Short-form 36 (SF-36), Anxiety Sensitivity Index (ASI), Beck Depression Inventory (BDI-II), and Prescription Drug Use Questionnaire (PDUQ)
5. Schedule future study visits
6. Blood draw (10 cc) to measure plasma morphine concentration to confirm subject is not taking morphine

Visits 2, 3 and 5

1. Vital signs will be taken
2. Urine sample will be collected for DOA and acetazolamide/creatinine measurement
3. Collect and count unused study medication and provide study medication for the next phase
4. Review daily pain and medication logs and provide subject with new logs
5. The following questionnaires will be completed: Pain Questionnaire, Short-form McGill Pain Questionnaire (SF-MPQ2), Short-form 36 (SF-36), Anxiety Sensitivity Index (ASI), Beck Depression Inventory (BDI-II), and Prescription Drug Use Questionnaire (PDUQ)
6. QST testing

Visits 4

1. Vital signs will be taken
2. Urine sample will be collected for DOA and acetazolamide/creatinine measurement
3. Collect and count unused study medication and provide study medication for the next phase
4. Review daily pain and medication logs and provide subject with new logs
5. The following questionnaires will be completed: Pain Questionnaire, Short-form McGill Pain Questionnaire (SF-MPQ2), Short-form 36 (SF-36), Anxiety Sensitivity Index (ASI), Beck Depression Inventory (BDI-II), and Prescription Drug Use Questionnaire (PDUQ)
6. Perform QST
7. Blood draw (10 cc) to measure plasma morphine concentration and biomarkers

Visit 6

1. Vital signs will be taken
2. Urine sample will be collected for DOA and acetazolamide/creatinine measurement
3. Collect and count unused study medication
4. Review daily pain and medication logs
5. The following questionnaires will be completed: Pain Questionnaire, Short-form McGill Pain Questionnaire (SF-MPQ2), Short-form 36 (SF-36), Anxiety Sensitivity Index (ASI), Beck Depression Inventory (BDI-II), Clinical Opioid Withdrawal Scale (COWS), and Prescription Drug Use Questionnaire (PDUQ)
6. Perform QST
7. Remuneration form completed

Phone Calls

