Trained study staff will call subjects at weeks 2, 4, 6 and 10 to monitor subject safety and compliance. Subjects will be asked about their pain, medication schedule, medication side effects, and overall health. Subjects will have an opportunity to ask questions and speak to a study physician.

Remuneration

Subjects will receive \$300 for completing the study, plus \$10 as a travel stipend for each office visit (up to \$370). Payment will be in the form of one check which will be mailed to the subject about 4-6 weeks after their last visit.

The following guidelines have been created for cases concerning pro-rated remuneration:

1. Subjects testing positive for illicit drugs or undisclosed prescriptions or subjects who are non-compliant with the study medication schedule will receive zero payment. Non-compliance will be determined by the study physicians on a case by case basis. We cannot define an objective set of criteria for non-compliance since every scenario will differ based on study phase, potential side effects, and subject reported information (such as incomplete logs or missed phone calls, and CleverCap discrepancy).
2. Subjects who do not complete the study through their own decision will receive full payment and the travel stipend for the visits attended.
3. Subjects who are withdrawn by an investigator by no fault of their own will receive full payment for the visits attended.

4. Subjects who fail to return the loaned CleverCaps will not receive payment to allow for the purchase of replacements.
5. Subjects who test positive for marijuana will be allowed to re-take the urine test in one week or at the next scheduled visit. If the second test is negative they will be allowed to continue in the study. If the second test is positive they will be withdrawn from the study and will not receive payment.

All prorated remuneration will be documented via progress notes and kept with the subject's research folder.

The pro-rated remuneration for visits attended is as follows:

1.

Screening Visit:	\$40 + \$10 travel stipend or parking pass
Visit 1:	\$50 + \$10 travel stipend or parking pass
Visit 2:	\$40 + \$10 travel stipend or parking pass
Visit 3:	\$40 + \$10 travel stipend or parking pass
Visit 4:	\$50 + \$10 travel stipend or parking pass
Visit 5:	\$40 + \$10 travel stipend or parking pass
Visit 6	\$40 + \$10 travel stipend or parking pass

b. Drugs to be used:

Dose of study medications

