duloxetine and placebo group. Subjects will be titrated onto the rescue medication and will be allowed to take up to two 15 mg instant release morphine pills/day, so that the total maximum dose of morphine (extended release + instant release) is 90 mg/day. Subjects will be tapered off the rescue morphine before they finish the study. To avoid overdosing, subjects will be instructed to wait at least 2 hours after taking their other study medication (extended release morphine or placebo) before taking the rescue dose. They will also be asked to wait at least 2 hours before taking the next dose of the study medication.

Medication schedule:

Subjects will participate in this 10 week study that consists of three phases: Phase I is the dose titration period of 4 weeks, Phase II is the dose maintenance period of 4 weeks, and Phase III is the dose taper period of 2 weeks. Study medications will be dispensed at weeks 1, 3, 5, 7, and 9. For the subject's safety, study medication for the titration and maintenance periods will be dispensed with up to an additional three days of medication; this will prevent medication withdrawal if the subject has to reschedule a visit. Subjects will take the medication according to the table below:

TITRATION PERIOD						
Week	Extended Release Morphine (15mg) or Placebo		Rescue medication: Instant Release Morphine (15 mg)	Week	Duloxetine or Placebo (30mg)	
	Morning	Evening			Evening	
1	0	1	≤1	1	1	
2	1	1	≤2	2	2	
3	1	2	≤2	3	2	
4	2	2	≤2	4	2	

MAINTENANCE PERIOD						
Week	Extended Release Morphine (15mg) or Placebo		Rescue medication: Instant Release Morphine (15 mg)	Week	Duloxetine or Placebo (30mg)	
	Morning	Evening			Evening	
5-8	2	2	≤2	5-8	2	

TAPER PERIOD						
Day	Extended Release Morphine (15mg) or Placebo		Day	Rescue medication: Instant Release Morphine (15 mg)	Day	Duloxetine or Placebo (30mg)
	Morning	Evening				
56-60	1	2	56-62	≤1	56-62	1
61-65	1	1	63, 65, 67, 69	0	63, 65, 67, 69	0
66-69	0	1	64, 66, 68	≤1	64, 66, 68	1

Study drug compliance

We will use the following methods to monitor subjects' compliance with the study medication:

1. We will provide study subjects with a log sheet to record their daily medication intake (date and time). Study subjects will be asked to bring the medication and log to each scheduled study visit. The medication will be counted to make sure the returned quantity matches the balance between total given and taken based on the log sheet.

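### No contact is scheduled after the end-of-week-10 visit, which falls about one day after the last extended-release morphine dose, so problems arising once subjects are off drug are not actively sought

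*Combined protocol and SAP*

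**What the plan says.** Section V.a (Study visits) lists "Seven office visits (screening visit, weeks 1, 3, 5, 7, 9, and end of week 10) and four follow up phone calls". The Phone Calls paragraph places the last call in week 10: "Trained study staff will call subjects at weeks 2, 4, 6 and 10 to monitor subject safety and compliance". On the content of the calls it says "Subjects will be asked about their pain, medication schedule, medication side effects, and overall health".

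On dosing, section V.b states that "Phase III is the dose taper period of 2 weeks". Its taper table covers days 56 to 69. Extended-release morphine or its placebo is taken through the evening of day 69. Duloxetine or its placebo, and the last permitted rescue tablet, end on day 68.

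The Visit 6 questionnaire list contains "Clinical Opioid Withdrawal Scale (COWS), and Prescription Drug Use Questionnaire (PDUQ". The drug use questionnaire is given at every office visit; the withdrawal scale (COWS) appears in no other visit's list. Visit 6 also has the depression inventory (BDI-II), a urine screen and collection of unused medication, and dispenses nothing.

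On exposure, the fifth inclusion criterion includes "Has not taken an opioid in the last 3 months", and section V.b sets rescue dosing "so that the total maximum dose of morphine (extended release + instant release) is 90 mg/day".

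Section IX.b requires study physicians to be paged for withdrawal symptoms, moderate-to-severe withdrawal scores, severe depression or signs of suicidality. It describes hand-over to the treating physician or emergency department, and keeps a physician on a pager at all hours. Sections V.c and V.d describe an automatic alert for admissions and emergency visits within the Partners network.

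**The concern.** The trial gives morphine to people who have not been taking an opioid, then tapers them off and ends follow-up almost at the last dose. Section VII.d names dependence and addiction as risks of morphine, and worsening depression and suicidality as risks of duloxetine, though not specifically as effects of stopping. The section IX.b paging rule needs an encounter at which symptoms or scores come to light; after Visit 6 none is planned.

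At stake is mainly subject safety: withdrawal, mood change or opioid use that begins after the last visit would be learned of only if the subject called or attended a hospital in the network. A lesser point is that opioid dependence and side-effect profile are secondary outcomes (section VI.b), and neither has a planned observation beyond Visit 6.

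**Working it through.** No sample-size formula applies; the check is calendar arithmetic on the taper table.

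**Reproducing the plan's timeline.** 4 + 4 + 2 = 10 weeks. Taper length: 69 − 56 + 1 = 14 days, the stated 2 weeks. Week 9 starts on day 56 = 8 × 7, so dosing starts on day 0 and week 10 is days 63 to 69.

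**Day of Visit 6.** No day is given.
- Read literally from the table numbering, the end of week 10 is day 69.
- Medication is dispensed at weeks 1, 3, 5, 7 and 9. If each visit opens its week, these are days 0, 14, 28, 42 and 56, and the next two-week step is 56 + 14 = 70. A visit that collects medication and dispenses none also fits day 70, because on day 69 an evening dose is still due.

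Day 70 is the more likely reading.

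**Dose by day**, in mg, for a subject at the full scheduled dose who takes every permitted rescue tablet:

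| Days | Extended-release (Groups 1, 2) | Rescue maximum | Total morphine, Groups 1, 2 | Total morphine, Group 3 | Duloxetine (Groups 2, 3) |
|---|---|---|---|---|---|
| 28–55 | 60 | 30 | 90 | 30 | 60 |
| 56–60 | 45 | 15 | 60 | 15 | 30 |
| 61–62 | 30 | 15 | 45 | 15 | 30 |
| 63, 65 | 30 | 0 | 30 | 0 | 0 |
| 64 | 30 | 15 | 45 | 15 | 30 |
| 66, 68 | 15 | 15 | 30 | 15 | 30 |
| 67, 69 | 15 | 0 | 15 | 0 | 0 |
| 70 | 0 | 0 | 0 | 0 | 0 |

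Extended-release reduction before Visit 6: (60 − 15)/60 = 75%.

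**Gap = day of Visit 6 − day of last dose.**

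| Visit 6 on | After extended-release (day 69) | After duloxetine and rescue (day 68) |
|---|---|---|
| Day 70 | 1 day | 2 days |
| Day 69 | 0 days | 1 day |

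With Visit 6 on day 70, Group 3 takes only placebo on day 69 and so has one complete day free of morphine and duloxetine. Groups 1 and 2 have none. With Visit 6 on day 69, no group has one. The week-10 call falls within days 63 to 69, so it adds nothing later. Scheduled contacts after Visit 6: 0.

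**Numbers concerned**, at the planned 20% dropout: 45 × 0.8 = 36 completers per group. That is 2 × 36 = 72 in Groups 1 and 2, and 3 × 36 = 108 in all, leaving 135 − 108 = 27 early leavers.

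**The case against.** The best defence is that the taper is gradual and watched. Extended-release morphine falls by three quarters under observation, with Visit 5, the week-10 call and Visit 6 in those two weeks. Paging is triggered by symptoms as well as by a score, so it can act at all three contacts. Section IX.b passes problems found by then to the treating physician, the emergency department, urgent care or primary care. All of this stands, and it rules out any claim that withdrawal goes unmonitored. It does not reach problems that begin after Visit 6.

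The remaining cover is passive. The pager depends on the subject. The alert sees only Partners hospitals, while section III.b also recruits from the local community, and section V.d describes it as serving subjects during participation, so its reach after Visit 6 is unclear. Some early leavers get extra contact: up to three taper visits for intolerance or noncompliance (section IX.b), and withdrawal monitoring after a marijuana dismissal (section V.a). No timing relative to the last dose is stated for either.

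Four stronger readings are tempting and are not supported:
- **Nobody has a drug-free day before the last contact.** With Visit 6 on day 70, Group 3 does.
- **All subjects may receive 90 mg/day of morphine.** That ceiling applies to Groups 1 and 2; Group 3 is limited to two 15 mg rescue tablets, 30 mg/day.
- **Visit 6 precedes the final dose.** This needs the less likely day-69 reading.
- **Residual duloxetine hides discontinuation effects at Visit 6.** The half-lives in section I.c invite this, but such a calculation needs dose and visit times that the documents do not give. The alternate-day doses on days 64, 66 and 68 also let the level fall low before Visit 6. Assuming 20:00 doses, a 10:00 visit and simple exponential decay, the load just before those doses is 0.7–7.1% of the maintenance peak over the stated half-lives, against 1.7–7.7% at Visit 6 on day 70. The argument adds little and is not relied on here.

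**Conclusion.** The point holds as a modest safety gap. On the likely day-70 reading, the last scheduled contact is 1 day after extended-release morphine in Groups 1 and 2, and 2 days after duloxetine and rescue where these are taken. The only planned withdrawal score is taken at that visit, and nothing scheduled follows. About 108 completers are concerned, 72 of them assigned extended-release morphine; for the 27 expected early leavers the timing of final contact is unstated.

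This rests on the taper table's day numbering, on dispensing visits opening their weeks, and on the plan's own dropout figure. No visit window is given, so an individual Visit 6 could fall later, but the plan does not provide for that.

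A reader might infer that the taper is unsafe or that harm after stopping is likely. The documents give no rate of events after the last dose, so neither can be concluded. The primary outcomes (VAS at weeks 0, 4, 8 and 10, and opioid dose) are unaffected.

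**What to change.** Add one scheduled safety call about one week after each subject's last dose (69 + 7 = day 76 for completers), for completers and for those finishing an early-withdrawal taper. To the existing call questions add:
- the withdrawal symptoms named in section IX.b;
- mood and suicidality;
- any opioid use;
- hospital or emergency visits at any site.

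Apply the section IX.b paging rule to this call, collect adverse events up to it, and report the number reached per group. Leave the week-10 outcome assessment unchanged.

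**Cost.** At most 135 short calls at planned enrolment, against 4 × 135 = 540 already planned (135/540 = 25% more), made by staff who already call subjects. It needs a minor amendment. The downside is about one more week of follow-up per subject and some non-response. Payment is "one check which will be mailed to the subject about 4-6 weeks after their last visit", so for completers the call comes while the study still has business with the subject; payment need not depend on it.

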The potential subject will be provided with information about the research through advertisements, Research Invitations, or reading a copy of the Consent Form. The potential subject can learn more about the study including potential benefits, risks, and discomforts by speaking with the study staff. The subject will be given as much time as needed to consider participating in the study. If the subject is eligible and decides to participate, he/she will be scheduled for a visit at the MGH Center for Translational Pain Research. At the first visit, the subject will read the Consent Form and then meet with a study physician via phone call to review and discuss the details of the study that are outlined in it. Any questions pertaining to the study will be answered at that time. If the subject agrees to participate, he/she will sign the Consent Form through a survey on REDCap with Adobe sign feature using a laptop provided or personal electronic device. The study physician will then log into REDCap right after and sign their signature. Two copies of the Consent Form will be printed with signatures from the REDCap website. The subject will take one copy and the other copy will be kept in his/her study folder. Subjects will have the option to meet with a study physician who is not their pain physician.

c. Treatment Assignment and Randomization

A total of 135 subjects will be enrolled for this double-blind, randomized study. Subjects will be randomized into three groups (n=45 subjects/group) using a computer-generated randomization protocol (Randomization.com).

- Group 1: morphine + placebo with acetazolamide
- Group 2: morphine + duloxetine with acetazolamide
- Group 3: placebo + duloxetine with acetazolamide

The duloxetine and placebo for duloxetine are specifically compounded with acetazolamide (15 mg), which will be used as a tracer to determine a subject's compliance with the study medication.

V. STUDY PROCEDURES

a. Study visits and parameters to be measured

Subjects will participate in a 10 week study consisting of three phases: Phase I is the dose titration period of 4 weeks, Phase II is the dose maintenance period of 4 weeks, and Phase III is the dose taper period of 2 weeks.

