Group 1: Extended release morphine (15 mg) + placebo with acetazolamide (15 mg): Subjects will be titrated onto extended release morphine until their pain level is reduced to a VAS ≤ 3 or until the maximal tolerable dose (up to 60 mg/day) is reached. The placebo will be a sugar pill and will be compounded with acetazolamide (15 mg).

Group 2: Extended release morphine (15 mg) + duloxetine (30 mg) with acetazolamide (15 mg): Subjects will be titrated onto extended release morphine until pain level is reduced to a VAS ≤ 3 or until the maximal tolerable dose (up to 60 mg/day) is reached. Subjects will be titrated onto duloxetine until they have reached 60 mg/day. The duloxetine will be compounded with acetazolamide (15 mg).

Group 3: Placebo + duloxetine (30 mg) with acetazolamide (15 mg) The placebo will be a sugar pill. Subjects will be titrated onto duloxetine until they have reached 60 mg/day. The duloxetine will be compounded with acetazolamide (15 mg).

Morphine placebo and duloxetine placebo will have similar weight and packaging to the true morphine and true duloxetine in order to maintain blinding for subjects and study staff. The morphine/morphine placebo pills will be packaged in a different colored capsule than the duloxetine/duloxetine placebo so subjects can differentiate between the two pills. All medications will be taken orally, and will be prepared, dispensed, and coded by the MGH Research Pharmacy. The assignment will not be disclosed to the study subject or study staff.

Rescue medication:

Subjects in all three groups will be asked to stay on the same non-opioid pain medications, if any, without change once the study starts. Although no progression of overall pain condition is expected for study subjects, there may be sporadic breakthrough pain on top of an otherwise stable pain condition (i.e., no worsening of underlying pathology). This would be more likely to occur in the

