2. Study medication vials will be secured with a CleverCap Pro which is a tamper resistant electronic cap that dispenses medication at a pre-set interval and a pre-set amount.

CleverCaps also record when the dose is dispensed so study staff will review these times and compare them to the subject's daily medication log.

3. The duloxetine and placebo for duloxetine are specifically compounded with acetazolamide (15 mg), which will be used as a tracer to determine a subject's compliance with the study medication. We will collect a urine sample at each visit and test for levels of acetazolamide and creatinine. An acetazolamide/creatinine ratio will be used to determine if the subject has been taking the study medication containing acetazolamide if the cut-off ratio is set at 1. The urine samples will be sent to WuXi AppTec for the acetazolamide analysis. Blood will also be drawn at two visits to monitor the morphine plasma level.

Noncompliance with medication and study visits, which affects the subject's health or data integrity, may require withdrawal from the study.

c. Electronic medical record

When subjects enroll in this study, a notation will be made in their electronic medical record, which associates the subject with the study. We will also upload a copy of their signed Consent Form. Once subjects are associated with the study, anytime they are admitted to a Partners Hospital or visit a Partners Hospital Emergency Department, the study doctors will be alerted electronically.

d. Hospital Admissions Alert System

MGH uses an electronic system that automatically alerts your study doctors if you are admitted to a Partners Hospital or if you visit a Partners Hospital Emergency Department. The study doctors can know if you experience any side effects or other problems while partaking in the study.

e. Devices to be used

Medoc Thermal Sensory Analyzer (TSA), a thermal quantitative sensory testing device. This device is FDA approved in diagnosing neuropathic pain syndromes. The MGH Bioengineering Department inspects this device annually.

f. Procedures/surgical interventions

QST is a commonly used pain assessment tool both for human pain studies and clinical diagnosis. The thermode-skin interface will change temperature at 1 °C/second from a baseline of 32 °C to a maximum of 53 °C. The subject can withdraw from the stimulation at any time. The following are examples of QST using heat stimulation.

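### On-treatment morphine results (plasma at Visit 4, urine at Visits 2 to 5) are not masked from blinded staff, although Group 3 has no scheduled morphine

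*Combined protocol and SAP*

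**What the plan says.** **Blinding.** Section IV.c describes a double-blind trial with 45 subjects in each of three arms. One arm is "Group 3: placebo + duloxetine with acetazolamide", so its morphine capsule is a sugar pill. Section V.b adds: "The assignment will not be disclosed to the study subject or study staff". The rest of the blinding text covers matched capsules and pharmacy coding. It does not mention laboratory results.

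**Urine.** Section V.a schedules a drug screen at every office visit, with this rule: "Subjects who are using illicit drugs detected by urine toxicology/drug screen including stimulants, benzos, alcohol, opioid (other than the study opioid), cocaine will be withdrawn". The assay and the form of the report are not described.

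**Plasma.** Section V.a states: "We will also measure plasma morphine concentration during the titration and maintenance phase to help validate morphine intake". Section V.b (Study drug compliance) counts the plasma level among its compliance methods. The visit lists place one draw at Visit 1, before dosing, and one at Visit 4 (week 7). No recipient of the value is named.

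**Rescue.** Subjects in all three arms "will be allowed to take up to two 15 mg instant release morphine pills/day".

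**Non-compliance.** Under Remuneration in V.a, study physicians judge it case by case, without fixed criteria, and "subjects who are non-compliant with the study medication schedule will receive zero payment". Section V.b says: "Noncompliance with medication and study visits, which affects the subject's health or data integrity, may require withdrawal from the study". Section IX.b is firmer and says that noncompliant subjects will be withdrawn.

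**Tracer.** Acetazolamide is compounded into both duloxetine and its placebo, so every arm receives it.

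**The concern.** A morphine assay used as a compliance check behaves differently by arm when one arm receives morphine placebo. Groups 1 and 2 should be positive if they take their capsules. Group 3 is positive only if rescue was taken recently. A blinded physician who sees a negative beside a complete log and cap record has two explanations to choose from: the subject is in Group 3, or the subject is not taking the drug.

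The first reading weakens the blind. VAS pain is a primary outcome, and staff also ask about pain and side effects and run the QST. The second reading can cost a compliant Group 3 subject payment or continued participation. Through this route compliant subjects would be lost from Group 3 only, which would distort the dropout comparison (a secondary outcome in VI.b) and the three-group comparisons of VAS and rescue dose.

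The acetazolamide tracer is present in every arm and so gives nothing away. The morphine checks have no equivalent protection.

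**Working it through.** The documents give no figure for this risk, so there is none to reproduce. The steps below show which visits matter and what a negative would mean under stated assumptions.

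**1. Informative visits.** Screening and Visit 1 precede the first dose. Visit 6 falls at the end of week 10, and the taper table ends at day 69, so Groups 1 and 2 may also be negative by then. That leaves Visits 2, 3, 4 and 5 for urine, and Visit 4 for plasma.

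**2. How strongly a negative points to Group 3.** Let p be the chance that a Group 3 subject is morphine-negative at a visit, and q the same chance in Groups 1 and 2. Both are assumed. Under 1:1:1 allocation the prior probability of Group 3 is 1/3, and

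P(Group 3 | negative) = (p/3) / (p/3 + 2q/3) = p / (p + 2q).

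| | q = 0 | q = 0.05 | q = 0.20 |
|---|---|---|---|
| p = 0.10 | 1.00 | 0.50 | 0.20 |
| p = 0.25 | 1.00 | 0.71 | 0.38 |
| p = 0.50 | 1.00 | 0.83 | 0.56 |

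A negative raises the probability above 1/3 only when p exceeds q. Certainty needs q = 0. Among subjects whose logs, counts and cap records show the capsules taken, q should be small, so the left-hand columns are the relevant ones. Over the p and q values in the table, a positive result is weak evidence: P(Group 3 | positive) runs from 0.20 to 0.36.

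**3. Chance of at least one negative in Group 3 over Visits 2 to 5.** If rescue use is fully correlated within a subject, the chance is p. If visits are independent, it is 1 − (1 − p)^4. Counts are out of 45.

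| p | Fully correlated | Independent |
|---|---|---|
| 0.10 | 10% (4.5) | 34% (15.5) |
| 0.20 | 20% (9) | 59% (26.6) |
| 0.30 | 30% (13.5) | 76% (34.2) |
| 0.50 | 50% (22.5) | 94% (42.2) |

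Section VI.d anticipates about 20% dropout. With 45 × 0.8 = 36 subjects, the extremes become 36 × 0.10 = 3.6 to 36 × 0.50 = 18 (correlated), and 36 × 0.344 = 12.4 to 36 × 0.9375 = 33.8 (independent).

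**4. Which comparisons are exposed.** Groups 1 and 2 both have scheduled morphine, so this route does not separate them. Section VI.b compares overall opioid dose between those two groups only. VAS, rescue dose and the secondary outcomes are compared across all three groups, and those involve Group 3.

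**The case against.** The strongest reply is that the documents never say that site staff receive a morphine result. A urine report that lists only non-study opioids would satisfy the withdrawal rule, and the plasma samples could be assayed later in a batch. This stands as far as it goes: a reader might infer that staff see a morphine-specific urine result at every visit, and no text states that. It does not remove the point. Plasma morphine is listed as a compliance method and study physicians judge compliance, so a value they never see would not serve that purpose during the trial. The urine rule also requires someone to separate morphine from other opioids. With no masking text, disclosure is the natural reading.

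Second, no rule acts on a morphine-negative urine. The urine compliance test is the acetazolamide/creatinine ratio, the examples of non-compliance given are incomplete logs, missed calls and cap discrepancies, and the physicians know that one arm takes morphine placebo. This also stands. Removal of compliant Group 3 subjects is possible but is not what the plan prescribes.

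Third, p is not documented. The protocol expects breakthrough pain to be more likely in Group 3, which favours a lower p, and rescue use probably persists within a subject, which favours the correlated column. The 34% to 94% range is therefore an upper scenario.

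Fourth, VAS is rated by the subject, nothing says that results are disclosed to subjects, and no text says that the same individuals read results and collect outcomes. Nor does any text separate those roles.

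**Conclusion.** The concern holds as a gap in the blinding plan. The protocol uses a morphine assay to check compliance in a trial with a morphine-placebo arm, and does not say who receives on-treatment results or how a negative is to be handled. A negative at Visits 2 to 5 with intact intake records is probabilistic evidence of Group 3, or may be misread as non-compliance.

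The number affected cannot be fixed from the documents. With p assumed at 10% to 50%, the share of Group 3 with at least one negative lies between 10% to 50% (visits fully correlated) and 34% to 94% (visits independent).

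Two stronger readings are tempting and not supported. One is that a negative identifies Group 3 outright; that needs no negatives at all in Groups 1 and 2. The other is that the blind fails for the whole trial. The central contrast, morphine with and without duloxetine, is not exposed by this route. What is at risk is the set of comparisons with Group 3 and the dropout outcome.

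**What to change.** Amend section V.a (Urine Screening and the visit lists) and the Study drug compliance part of V.b to state that:

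- on-treatment plasma morphine values are withheld from blinded staff until database lock;
- the on-study urine report to the site covers non-study opioids and the other drug classes only, and any morphine line is held by the Research Pharmacy or the laboratory;
- blinded compliance review rests on the measures that do not differ by arm and are already collected: acetazolamide/creatinine ratio, pill counts, CleverCap records and logs.

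The pharmacy should not send site staff a flag for results inconsistent with assignment. In Groups 1 and 2 any negative would raise it, while in Group 3 only a positive without logged rescue would, so the flag could itself disclose the arm.

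Two related texts need reconciling. Section V.a places plasma sampling in the titration and maintenance phases, while the visit lists give a pre-dose draw and a week-7 draw. Sections V.b and IX.b differ on whether non-compliance may or will lead to withdrawal.

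The cost is changed routing for up to 135 × 4 = 540 urine reports, and loss of real-time morphine compliance information at the site. The tracer sits in the duloxetine capsule, so intake of the morphine capsule would be judged during the trial from counts, caps and logs alone; plasma values remain available after lock. If the urine screen is a point-of-care panel, some extra handling is needed so that blinded staff do not read the opioid line. No visits or tests are added, and dosing is untouched.
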